6.1 Number of Sites and Subjects

Subjects will be enrolled at up to 8 investigational sites (Sites) in the United States to ensure that data is collected from approximately 30 subjects who undergo laser ablation.

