6.3.1 Study Inclusion Criteria

Subjects must meet all of the following inclusion criteria:

1. Diagnosis of unilateral medial temporal lobe epilepsy (MTLE) confirmed clinically and with either (1) ictal scalp recording and MRI evidence of mesial temporal sclerosis or (2) intracranial ictal onset consistent with hippocampal origin
2. Subject's seizures are distinct, stereotypical events that can be reliably counted.
3. Based on medical record, history of an average of at least 1 complex partial or secondarily generalized seizure compatible with MTLE per month for a minimum of the last 12 months prior to the Baseline visit (i.e., at least 12 qualifying seizures in the 12 months prior to the Baseline visit). *(Seizures occurring during inpatient assessment in an epilepsy monitoring unit should not be included in the average).*
4. Subject is on stable antiepileptic drugs (AEDs) for 30 days prior to the Baseline visit and compliant with medication use (as reported by the subject). Stable is defined as no new or discontinued AEDs and no changes to AED total daily dose. *(Exception: (1) temporary changes or discontinuation of AEDs for the purposes of diagnostic or medical procedures during the 30 days preceding the Baseline visit and (2) acute, intermittent use of benzodiazepines or other rescue medications.)*
5. Subject has met the criteria for a medial temporal lobe resection based on the Site's standardized pre-surgical evaluation.
6. Subject is deemed a LITT candidate by the center's epilepsy evaluation team.
7. Subject is 18 years or older at the time of consent.
8. Subject can be reasonably expected to maintain a seizure diary alone or with the assistance of a caregiver.
9. If female, must be postmenopausal, surgically sterile, or, if of childbearing potential, have a serum pregnancy test with a negative result at the Baseline visit and practicing effective contraception.³
10. Subject or legally authorized representative is able to provide appropriate consent to participate.
11. Subject is able to complete regular office and telephone appointments per the protocol requirements.
12. Subject speaks English or Spanish as a primary language. If Spanish, the Site must be able to provide a translated (IRB-approved) consent form and the Site's neuropsychologist must be willing and able to assess the subject in Spanish.

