7 STUDY METHODOLOGY

7.1 Trial Summary

Subjects who meet the study eligibility criteria and sign the informed consent form (ICF) will undergo a Baseline visit for initial evaluations, testing and collection of demographics and medical history.

The LITT surgical procedure will be performed within 30 days of the Baseline visit. After the procedure, subjects will be seen for a brief visit prior to discharge from the hospital and again at the Day 14 visit. Subject visits will continue with office visits at Months 1, 3, 6, 9 and 12. After the Month 12 visit, subjects will have semi-annual office visits, at Months 18 and 24. Starting at Month 2, subjects will have

⁴ Exclusion criteria may need to be evaluated after obtaining informed consent, if it not part of the Site's standard of care for epilepsy management and/or surgery evaluation.

interim monthly phone calls (the months that the subject is not seen for an office visit). Investigators will keep AEDs stable through the Month 12 visit.

The study design is outlined in Figure 3.

[figure not shown]

Figure 3: Study Design Schema

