7.5 Schedule of Visits and Testing Requirements

Table 1 and Table 2 outline the visits, visit windows, and testing requirements at each evaluation time point.

Table 1: Visits and Testing Requirements and Data Collection Summary (Baseline through Month 12)

Visit Window	Baseline			LITT Proc.	DC	Post-Procedure												
	Within 7 days of enrollment	Day of DC	Within 30 days of Baseline ¹			Day 14	Mo. 1	Mo. 2	Mo. 3	Mo. 4	Mo. 5	Mo. 6	Mo. 7	Mo. 8	Mo. 9	Mo. 10	Mo. 11	Mo. 12
	Visit Type	Icon 1	Icon 2	Icon 3	Icon 4	Icon 5	Icon 6	Icon 7	Icon 8	Icon 9	Icon 10	Icon 11	Icon 12	Icon 13	Icon 14	Icon 15	Icon 16	Icon 17
Inclusion and exclusion criteria	✓																	
Informed consent	✓																	
Demographics	✓																	
Medical, surgical & epilepsy history	✓																	
QOLIE-31	✓													✓				✓
Medication review (epilepsy and non-epilepsy)	✓					✓	✓	✓	✓	✓	✓	✓	✓	✓	✓	✓	✓	✓
Physical exam	✓						✓	✓						✓				✓
Neurological exam	✓						✓	✓	✓				✓			✓		✓
Formal visual field testing	✓													✓				
Serum pregnancy test (if female of child-bearing potential)	✓																	
Neuropsychological testing ²	✓ ³												✓		✓			✓
Functional assessment	✓							✓	✓				✓		✓		✓	✓
Seizure classification assessment	I												U		U			U
Seizure diary	T					T/D	C/D	C/D	C	C/D	C	C	C/D	C	C	C/D	C	C/D
Adverse event monitoring						✓	✓	✓	✓	✓	✓	✓	✓	✓	✓	✓	✓	✓
Treatment criteria																		
LITT treatment						✓												
MRI						✓	✓ ⁴							✓				
Surgical pain VAS						✓	✓							✓		✓		✓
Surgical outcome classifications ⁵													✓		✓			✓
Subject satisfaction													✓					✓

Abbreviations: C, collect; D, dispense; DC, discharge; I, initial; LITT, laser interstitial thermal therapy; Mo., month; MRI, magnetic resonance imaging; proc., procedure; QOLIE-31, Quality of Life in Epilepsy - 31; T, training; U, update; VAS, visual analog scale.

¹ Surgery may be performed >30 days after the Baseline Visit if needed to accommodate neuropsychological test scheduling.

² See Appendix C for details of the neuropsychological testing at each visit. These can be performed on a separate day than the Baseline visit.

³ Prior neuropsychological testing may be used for Baseline if the testing was conducted within 6 months prior to the Baseline visit and there were no significant changes to the subject's AEDs or changes to the subject's clinical condition that may affect cognitive function.

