7.6 Procedures and Subject Assessments

7.6.1 Baseline Visit

Prior to consenting patients for the study, Site personnel will evaluate potential candidates by reviewing the patient medical records against the study eligibility criteria. It is expected that the medical records will contain adequate information to determine if the patient meets these criteria. Potential patients will be asked to complete the informed consent process.

The following evaluations and assessments will be performed at this visit:

- Demographics
- Medical, surgical and epilepsy history
 - Epilepsy history will include collection of 12 months of retrospective seizure frequency data; data from the 3 months prior to the Baseline visit will be used for eligibility determination. See Appendix B for more details.
- Quality of Life in Epilepsy - 31 (QOLIE-31). It is preferred that the subject completes the questionnaire prior to any other baseline tests.
- Medication review, including collection of 12 months of retrospective epilepsy medication data (as available) to qualitatively assess medication stability prior to the NeuroBlate procedure. See Appendix A for more details.
- Physical exam
- Neurological exam
- Visual field testing (automated perimetry)
- Serum pregnancy test (if female and of childbearing potential)
- Neuropsychological testing (see Appendix C).
- Functional assessment (including employment status, education, living arrangements, driving status)
- Seizure classification assessment
- Seizure diary training

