7.6.2 LITT Procedure

An MRI will be performed prior to surgery to determine trajectory and frame/arc settings. The LITT procedure will be performed per the IFU. Adverse events that occur during the procedure will be collected.

Postoperatively, the subject should be managed per the institution's standard of care for subjects receiving LITT. This includes monitoring of the subject's neurological status as it relates to possible intraoperative or postoperative adverse events (including intracranial hemorrhage).

Subjects experiencing a failed LITT treatment attempt (stopping the procedure prior to thermal delivery) will be followed for 1 month post-procedure for adverse events.

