11.1 Risks

As with any surgical procedure, the NBS involves some risks. The following potential risks or discomforts may be associated with the surgical procedure or the NBS. In addition, the list includes possible risks associated with the use of the NBS in an epilepsy population.

The frequency and severity of adverse events can vary, and may necessitate additional medical intervention, including surgery.

Agitation	Deep venous thrombosis	Obtundation
Anemia	Depression	Paralysis
Brain aneurysm	Difficulty hearing	Personality or cognitive changes (e.g. mood, memory, attention and thinking ability)
Anxiety	Difficulty speaking	Permanent neurological deficit
Aphasia	Difficulty swallowing	Pneumonia
Ataxia or loss of body coordination	Difficulty walking	Pain at incision site
Atelectasis	Hypotension	Pulmonary or other air embolism
Bacteremia or sepsis	Increased seizures	Reaction to anesthesia or other drugs
Bleeding into or around the brain	frequency/duration or severity, new seizure type, or status epilepticus	Stroke or transient ischemic attack (TIA)
Blurry vision/visual disturbance	Infection, local or generalized	Sudden unexpected death in epilepsy (SUDEP)
Cerebral infarction	Injury to blood vessels	Thromboembolism
Coma	Injury to brain tissue	Tingling or numb sensations in the body
Complete or incomplete hemiparesis	Insomnia	Tissue damage
Death	Intestinal toxicity	Unconsciousness
Decreased energy	Loss of mental function	Wound dehiscence
Drowsiness	Muscle weakness	
Edema	Myocardial infarction	
Failure of central regulation	Nausea/vomiting	
Fever	Nerve paralysis	
Headache		
Hypertension		

Additional possible risks from the evaluations required during this study (but not directly related to the use of the NBS) include:

Laboratory Testing Risks

For the pregnancy test, a blood sample will be taken by inserting a needle into a vein in the arm. Some risks of this procedure include fainting, infection, bruising, formation of a blood clot, pain, and/or bleeding at the site of the needle puncture.

Pregnancy Risks

The effects of LITT during pregnancy are unknown, and it is possible that harmful side effects could occur to both the mother and unborn child. For this reason, pregnant subjects are excluded from participation in this study. If the subject is a woman of childbearing age capable of becoming pregnant, they will be given a pregnancy test prior to entry into the study and again prior to the procedure.

Neuropsychological Testing Risks

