The purpose of this Statistical Analysis Plan (SAP) is to document analyses that are planned for the FLARE study before they are performed (*pre-specified analyses*). The results of the analyses documented here are to be presented in the clinical study final report. Selected analyses may also be presented in interim reports, DSMB reports, and manuscripts reporting study results, as deemed appropriate by the authors. Additional analyses of the study data beyond the analyses pre-specified in this plan are expected, therefore the Statistical Analysis Plan does not preclude ad hoc analyses that may provide additional useful description of the performance of the investigational device.

2 Scope

This SAP should be read in conjunction with the Clinical Study Protocol (CL10054) and Case Report Forms (MON-CRF-1001 through MON-CRF-1030). Changes to the versions of the Clinical Study Protocol (protocol) and Case Report Forms (CRFs) cited above may necessitate updates to the SAP.

3 Applicable Documents

Document Number	Document Title
CL10054	Monteris FLARE Clinical Study Protocol, Rev A
MON-CRF-1001 through MON-CRF-1030	Monteris FLARE Study Case Report Forms
NAMSA STATSOP-002	Statistics Standard Operating Procedure – Statistical Analysis Plan

4 Software

Statistical analyses, tables, listings, and figures will be primarily produced using SAS statistical software (SAS Institute, Cary, NC), version 9.2 or later, or another validated statistical software package.

5 Abbreviations

The following is a list of abbreviations used in the body of this document.

ADE	adverse device effect
AE	adverse event
AED	antiepileptic drug
BVMT-R	Brief Visual Memory Test – Revised
BNT-60	Boston Naming Test – 60 item version
CEC	Clinical Events Committee
DSMB	Data Safety and Monitoring Board
CRF	case report form
ICF	informed consent form
ICH	International Conference on Harmonization
IDE	Investigational Device Exemption
IQ	intelligence quotient
ILAE	International League Against Epilepsy
LITT	laser interstitial thermal therapy
MRI	magnetic resonance imaging

MTLE	mesial temporal lobe epilepsy
NBS	NeuroBlate® System
QOLIE-31	Quality of Life in Epilepsy – 31 item version
RAVLT	Rey Auditory Verbal Learning Test
SAE	serious adverse event
SOP	standard operating procedures
UADE	unanticipated adverse device effect
USADE	unanticipated serious adverse device effect
VAS	visual analog scale
WAIS-IV	Wechsler Adult Intelligence Scale-IV
WMS-IV	Wechsler Memory Scale-IV

6 Design

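### Section 11.1 says there will be a second pregnancy test before the procedure, but the protocol's eligibility and visit sections place only the Baseline test

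*Protocol*

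**What the plan says.** Protocol section 11.1, under Pregnancy Risks, describes the effects of LITT in pregnancy as unknown, with possible harm to mother and unborn child, and gives that as the reason pregnant women are excluded. It then says of women who could become pregnant that "they will be given a pregnancy test prior to entry into the study and again prior to the procedure".

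The eligibility and visit sections read differently:

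- Inclusion criterion 9 (section 6.3.1, repeated in the synopsis) says that a woman of childbearing potential must "have a serum pregnancy test with a negative result at the Baseline visit and practicing effective contraception".
- Section 7.6.1 lists the serum test among the Baseline assessments.
- Section 7.6.2 covers the procedure itself. Its one named pre-operative investigation is imaging: "An MRI will be performed prior to surgery to determine trajectory and frame/arc settings". No pregnancy test appears.

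On timing, section 7.1 says "The LITT surgical procedure will be performed within 30 days of the Baseline visit". Footnote 1 to Table 1 (section 7.5) relaxes this: "Surgery may be performed >30 days after the Baseline Visit if needed to accommodate neuropsychological test scheduling".

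**The concern.** A test done again before the procedure is a second test, so the Baseline test cannot serve as both. Yet no eligibility or visit section of the current protocol (Revision B) says when the second test is done, what kind it is, or what happens if it is positive. A coordinator who follows sections 7.5 and 7.6 to the letter would not do it.

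What is at stake is subject safety and the protocol's consistency with itself. The protocol takes fetal risk seriously: besides the exclusion, section 9.1 counts fetal distress, fetal death and congenital anomaly among serious outcomes. A negative Baseline test and effective contraception lower the risk. They do not cover a pregnancy that begins, or first becomes detectable, between Baseline and surgery.

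**Working it through.** No statistical calculation applies. The check is a comparison of every place that mentions, or would be expected to mention, pregnancy testing before LITT.

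| Place | Pregnancy tests | When |
|---|---|---|
| Protocol 11.1 | 2 | before entry, and again before the procedure |
| Protocol synopsis and 6.3.1, criterion 9 | 1 | Baseline |
| Protocol 7.6.1 | 1 | Baseline |
| Protocol Table 1, pregnancy-test row | 1 tick | reads as Baseline |
| Protocol 7.6.2 (LITT procedure) | 0 | – |
| Protocol 7.7 (additional LITT) | 0 | – |
| SAP Table 1 | 2 ticks | read as Week -12 and Week 0 |

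Column positions in the extracted tables are not reliable, so the finding does not rest on Table 1. Its single tick agrees with criterion 9 and section 7.6.1.

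**Gap from the placed test to surgery.** Under section 7.1 it is 0 to 30 days. Under footnote 1 it may exceed 30 days, and no maximum is stated.

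**Probable origin (inference).** The SAP lists as its governing protocol "Monteris FLARE Clinical Study Protocol, Rev A". Its Table 1 has four pre-procedure visits, Week -12 to Week 0, with LITT within 30 days of Week 0. Nominally, before visit windows:

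- Week -12 to Week 0: 12 × 7 = 84 days.
- First test to LITT: 84 + 0 = 84 days to 84 + 30 = 114 days.
- Second test (Week 0) to LITT: 0 to 30 days.

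In that schedule a second test had an obvious purpose: it cut the gap from 84–114 days to 0–30 days. Revision B has a single Baseline visit instead, and the section 11.1 sentence may have been carried over. There are other signs of carry-over. Table 1 of the current protocol keeps a treatment-criteria row with no ticks as extracted, and SAP section 10 cites a protocol section 6.4, whereas section 6 of Revision B ends at 6.3. Neither document says whether the second test was dropped on purpose.

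**How many women.** Let n be the number of treated women of childbearing potential. It is not given. Section 6.1 plans for "approximately 30 subjects who undergo laser ablation", so n lies between 0 and about 30. A pre-procedure test adds 1 × n tests. The documents give no basis for estimating how many would be positive.

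**The case against.** The strongest reply concerns weight. In the ordinary case Revision B has a test 0 to 30 days before LITT, and so did the schedule in the SAP, where the last test was at Week 0. On that comparison the current protocol is weaker mainly where footnote 1 applies, and that footnote is a narrow exception for scheduling neuropsychological tests. Effective contraception is also required. No endpoint, analysis set or sample-size figure depends on the point. All of this stands and limits the size of the finding.

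A second reply is that section 11.1 is itself part of the protocol, which investigators sign to follow, so the safeguard exists and only a cross-reference is missing. The case report forms, training plan, instructions for use and hospitals' own pre-operative routines were not available, and any of them might prompt the test. That is fair as far as it goes: one cannot say sites would in fact omit it. But a sentence in a risk section that gives no visit, no test type and no action on a positive result is a poor substitute for an entry in the schedule. The standard-of-care clause in section 7.6.2 covers postoperative management only.

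Third, the link to Revision A is an inference, since that version is not among the documents. The absence of a delay footnote in the SAP's table does not show that Revision A lacked one. This is accepted. The contradiction lies within Revision B and does not depend on how it arose.

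**Conclusion.** The concern holds. Section 11.1 states two tests, while criterion 9 and section 7.6.1 place one and section 7.6.2 places none. Confidence in the mismatch is high because it is visible in the running text without relying on the tables.

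Its practical size is modest. The exposed interval is 0 to 30 days, open-ended under footnote 1, for between 0 and about 30 women. The clinical yield of a second test cannot be estimated, and the statistical results are untouched. It is still more than an editorial slip, because following the visit sections exactly would leave out a fetal-safety check that the protocol says will be done. It should be corrected.

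**What to change.** **Preferred.** Add a line to section 7.6.2 requiring a negative pregnancy test before LITT for women of childbearing potential, and mark it in the procedure column of Table 1. Section 11.1 gives no interval, so the new line should state one. The cost is one line, one table entry and one routine test per eligible woman (0 to about 30 in all), with the result in hand before surgery. Section 11.1 already commits the study to this test.

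**Alternative.** If the sponsor deliberately merged the two tests in Revision B, correct section 11.1 to state a single test at Baseline. That costs one sentence and no tests. It is the less safe choice while footnote 1 sets no upper limit on the delay.

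**Optional.** Require the same test before a repeat LITT under section 7.7. Section 11.1 does not promise this, so it is a suggestion and not part of the correction.

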11.2 Methods to Minimize Risk

To mitigate the risks above, Monteris will work with neurosurgeons trained specifically in NeuroBlate techniques, train all study personnel and provide device labeling that contains all precautions, warnings and contraindications. The loud knocking sound during the MRI may be dimmed with the wearing of earplugs.

11.3 Benefits

There are no guaranteed benefits from participation in this study; however, it is possible that treatment with the study device may have the following benefits:

- The subject may experience a decrease in seizure frequency
- The subject may experience an improvement in their quality of life
- The subject may experience an improvement in their neuropsychological functioning

11.4 Alternative Treatment

There is no obligation for a subject to take part in this study. Alternative treatments may include:

- Undergoing the LITT procedure without participation in the study
- Undergoing a different surgical intervention (other than LITT)
- Continued medical (non-surgical) management

Each subject's doctor will inform the subject as to what alternative methods are available.

12 ADMINISTRATIVE PROCEDURES

12.1 Contact Information

The CRO will maintain a document with the contact information for all clinical study personnel participating in the study, including those listed below:

- Sponsor
- CRO
- Sites (principal investigator (PI), sub-investigator(s), study coordinators, neuropsychologists, and IRB chairperson
- Core Laboratory
- DSMB
- CEC

12.2 Site Selection

The Sponsor and/or CRO will assess each potential Site to ensure the investigators and his/her staff meet the following criteria:

- The Site is a current user of the NeuroBlate System
- The Site has an epileptologist that can act as principal investigator
- The Site has a neurosurgeon with experience using LITT for MTLE/MTS epilepsy patients
- The investigators are qualified by experience and training
- The Site has a neuropsychologist/neuropsychometrist
- The Site has adequate support staff responsible for fulfilling the clinical study requirements specified in the study protocol
- The Site is a level III or level IV epilepsy center based on the National Association of Epilepsy Center's guidelines
- The Site has experience doing epilepsy clinical studies
- The Site has adequate access to epilepsy patients specified in the study protocol
- The Site is not participating in another laser-based MTLE/MTS epilepsy clinical study that is currently enrolling subjects; studies that have completed enrollment and are in the subject follow-up phase would not exclude the site from participation in the FLARE study.
- The investigators are not on the FDA disqualified or debarred list

12.3 Site Training

Site personnel will be trained per the study-specific Training Plan. All Site personnel will undergo training prior to performing any study-related procedures. All training will be documented.

Existing Site personnel who have been delegated *new* tasks and new Site personnel will undergo training as designated in the Training Plan.

